#### 7.1.1 Solicited Adverse Events

The term “reactogenicity” refers to solicited signs and symptoms (“solicited adverse events”) occurring in the hours and days following a vaccination, to be collected by the subject for 7 consecutive days, using a pre-defined Subject Diary.

The following solicited adverse events are included in the Subject Diary. Each adverse event is to be assessed using the scoring system reported in parentheses below:

#### **Solicited local adverse events:**

The list of solicited local (injection site) adverse events is:

- Pain

- Erythema (mm)
- Swelling (mm)
- Warmth
- Induration (mm)
- Ecchymosis (mm)

Injection site erythema, swelling, induration and ecchymosis will be categorized based on the linear measurement of these events.

Injection site pain and warmth will be summarized according to none, mild (transient with no interference in normal daily activity), moderate (some interference in normal daily activity) or severe (unable to perform normal daily activity).

**Solicited systemic adverse events:**

The list of solicited systemic adverse events is:

- Chills
- Generalized myalgia
- Malaise
- Nausea
- Headache
- Fatigue
- Body rash
- Generalized arthralgia

Systemic events (except body rash) occurring up to day 7 after vaccination will be summarized according to: none, mild (transient with no interference in normal daily activity), moderate (some interference in normal daily activity) or severe (unable to perform normal daily activity). Body rash occurring up to day 7 after vaccination will be summarized according to: none (no rash), mild (localized area of the skin, or only one extremity), moderate (moderate area of the skin, or two or more body regions, without whole body involvement), or severe (most of the skin).

### **Other solicited reactions:**

- Body temperature for fever (preferably oral, captured daily as measurements in degrees Celsius)
- Use of analgesics/antipyretics

Body temperature will be summarized based on the measurement and grade.

Use of analgesics/antipyretics will be summarized as “for treatment” or “for prophylaxis”. Each local and systemic reaction will also be categorized as none vs. present.

The study staff must review the data entered into the Subject Diary as described in [section 3.4.2, Tools Used for Data Collection](#) and [section 5.3.1, Follow-up Clinic Visit\(s\)](#).

Note: Any solicited adverse event that meets any of the following criteria must be entered into subjects’ source document (see [section 9.1, Source Documentation](#)) and also as an adverse event on the Adverse Event CRF:

- Solicited local or systemic adverse event that continues beyond day 7 after vaccination.
- Solicited local or systemic adverse event that leads to a visit to a healthcare provider (medically attended adverse event, see [section 7.1.3, Evaluation of Adverse Events](#)).
- Solicited local or systemic adverse event leading to the subject withdrawing from the study or the subject being withdrawn from the study by the investigator (adverse event leading to withdrawal, see [section 7.1.3, Evaluation of Adverse Events](#)).
- Solicited local or systemic adverse event that otherwise meets the definition of a serious adverse event (see [section 7.1.4, Serious Adverse Events](#)).

### **7.1.2 Unsolicited Adverse Events**

An unsolicited adverse event is an adverse event that was not solicited using a Subject Diary and that was spontaneously communicated by a subject who has signed the informed consent.

Potential unsolicited AEs may be medically attended (defined as symptoms or illnesses requiring hospitalization, or emergency room visit, or visit to/by a health care provider), or were of concern to the subject. In case of such events, subjects will be instructed to contact the site as soon as possible to report the event(s). The detailed information about the reported unsolicited AEs will be collected by the qualified site personnel during the interview and will be documented in the subject’s records.

Unsolicited AEs that are not medically attended nor perceived as a concern by subjects will be collected during interview with the subject and by review of available medical records at the next visit (see section 5.3, [Post-vaccination Visit\(s\)](#)).

### 7.1.3 Evaluation of Adverse Events

Every effort should be made by the investigator to evaluate safety information reported by a subject for an underlying diagnosis and to capture this diagnosis as the event in the AE page. In other words, the practice of reporting only symptoms (e.g., “cough” or “ear pain”) are better reported according to the underlying cause (e.g., “asthma exacerbation” or “otitis media”).

The severity of events reported on the Adverse Events CRF will be determined by the investigator as:

Mild: transient with no limitation in normal daily activity.

Moderate: some limitation in normal daily activity.

Severe: unable to perform normal daily activity.

The relationship of the study treatment to an AE will be determined by the investigator based on the following definitions:

#### 1. Not Related

The AE is not related to an investigational vaccine if there is evidence that clearly indicates an alternative explanation. If the subject has not received the vaccine, the timing of the exposure to the vaccine and the onset of the AE are not reasonably related in time, or other facts, evidence or arguments exist that reasonably suggest an alternative explanation, then the AE is not related.

#### 2. Possibly Related

The administration of the investigational vaccine and AE are considered reasonably related in time and the AE could be explained by exposure to the investigational vaccine or by other causes.

#### 3. Probably Related

Exposure to the investigational vaccine and AE are reasonably related in time and no alternative explanation has been identified.

The relationship of the study treatment to an unsolicited AE will be determined by the investigator.

Note: solicited AEs will not be evaluated for relationship to study treatment. Grading for severity of solicited local and systemic AEs is described in [section 7.1.1, Solicited Adverse Events](#).

Adverse events will also be evaluated by the investigator for the co-existence of any of the other following conditions:

- “Medically attended adverse event”: an adverse event that leads to a visit to a healthcare provider.
- AEs leading to withdrawal: adverse events leading to study or vaccine withdrawal.

All AEs, regardless of severity, will be monitored until resolution or until the investigator assesses them as chronic or stable. All subjects experiencing AEs - whether considered associated with the use of the study vaccine or not - must be monitored until symptoms subside and any abnormal laboratory values have returned to baseline, or until there is a satisfactory explanation for the changes observed, or until death, in which case a full pathologist’s report should be supplied, if possible. The investigator’s assessment of ongoing Adverse Events at the time of each subject’s last visit should be documented in the subject’s medical chart.

#### 7.1.4 Serious Adverse Events

A serious adverse event (SAE) is defined as any untoward medical occurrence that at any dose results in one or more of the following:

- Death.
- Is life-threatening (i.e., the subject was, in the opinion of the investigator, at immediate risk of death from the event as it occurred); it does not refer to an event which hypothetically might have caused death if it were more severe.
- Required or prolonged hospitalization.
- Persistent or significant disability/incapacity (i.e., the event causes a substantial disruption of a person’s ability to conduct normal life functions).
- Congenital anomaly/or birth defect.
- An important and significant medical event that may not be immediately life threatening or resulting in death or hospitalization but, based upon appropriate medical judgment, may jeopardize the subject or may require intervention to prevent one of the other outcomes listed above.

Adverse events which do not fall into these categories are defined as non-serious.

It should be noted that a severe adverse event need not be serious in nature and that a serious adverse event need not, by definition, be severe.

Serious adverse events will be captured both on the Vaccines Serious Adverse Event (VSAE) form as well as on the AE CRF. All SAEs will be evaluated by the investigator for relationship of the event to study vaccine. SAEs that are judged to be possibly or probably related to the study vaccine should be reported to the Sponsor as related/suspected events.

The relationship of the study treatment to an SAE will be determined by the investigator based on the following definitions:

#### 1. Related/suspected

The SAE is judged by the investigator to be possibly or probably related to the study vaccine on the AE CRF page (see [section 7.1.3, Evaluation of Adverse Events](#)).

#### 2. Not Related

The SAE is not related if exposure to the study vaccine has not occurred, **or** the occurrence of the SAE is not reasonably related in time, **or** the SAE is considered unlikely to be related to use of the study vaccine, i.e., there are no facts (evidence) or arguments to suggest a causal relationship.

The relationship of the study vaccine to an SAE will be determined by the investigator.

In addition, SAEs will be evaluated by the Sponsor or designee for “expectedness.” An unexpected AE is one that is not listed in the current Summary of Product Characteristics or the Investigator’s Brochure or an event that is by nature more specific or more severe than a listed event.

In addition, a pre-existing event or condition that results in hospitalization should be recorded on the Medical History CRF. If the onset of an event occurred before the subject entered the study (e.g., any pre-planned hospitalization for conditions like cosmetic treatments or for non-emergency routine visits for a pre-existing condition), the hospitalization would not lead to an AE being classified as serious unless, in the view of the investigator, hospitalization was prolonged as a result of participation in the clinical study or was necessary due to a worsening of the pre-existing condition.

#### **7.1.4.1 Adverse Events of Special Interest**

AESIs are not assessed during the study.

### 7.1.5 Methods for Recording Adverse Events and Serious Adverse Events

Findings regarding Adverse Events must be reported on an Adverse Events CRF, as specified in [section 7.1.1, Solicited Adverse Events](#), and on the VSAE form, if applicable, which is part of the Investigator Site File. All findings in subjects experiencing AEs must be reported also in the subject's source document.

All SAEs which occur during the course of the study, whether considered to be associated with the study vaccination or not, must be reported **within 24 hours of the site becoming aware of the event** to GSK or its designee. Specific instructions and contact details for collecting and reporting SAEs to GSK will be provided to the investigator.

All SAEs are also to be documented on the Adverse Events CRF. Any medication or other therapeutic measures used to treat the AE will be recorded on the appropriate CRF(s) in addition to the outcome of the AE.

After receipt of the initial report, representatives of GSK or its designee will contact the investigator if it is necessary to obtain further information for assessment of the event.

All SAEs must be reported by the investigator to her corresponding EC and applicable regulatory authority in accordance with institutional policy/regulatory requirements and adequate documentation of this notification must be provided to the Sponsor.

GSK or its designee must also comply with the applicable regulatory requirement(s) related to the reporting of suspected unexpected serious adverse vaccine reactions (also known as SUSARs) to the regulatory authority and the EC. If a SUSAR or other safety signal relating to use of one of the study vaccines is reported to GSK or its designee, the Sponsor will communicate the information to the investigator and the investigator will be responsible for submitting this information to the EC and other relevant authorities.

#### 7.1.5.1 Post-Study Events

Any SAE that occurs outside of the protocol-specified follow-up period and considered to be caused by the study vaccine must be reported to GSK or its designee. These SAEs will be processed by GSK or its designee as during the course of the study, until 6 months post LSLV. Instructions and contact details for collecting and reporting these suspected SAEs will be provided to the investigator.

### 7.1.6 Pregnancies

To ensure subjects' safety, each pregnancy in a subject after study vaccination must be reported to GSK or delegate within 72 hours of the site learning of its occurrence. If the subject agrees to submit this information, the pregnancy must be followed to determine

outcome, including spontaneous or voluntary termination, details of the birth, and the presence or absence of any birth defects, congenital abnormalities, or maternal and/or newborn complications. This follow-up should occur even if intended duration of safety follow-up for the study has ended.

Pregnancy data must be recorded on a Pregnancy Report CRF (initial report) and Pregnancy Follow-Up CRF (outcome report) and reported to GSK or delegate. Instructions and contact details for submitting the Pregnancy CRFs will be provided to the investigator.

Any pregnancy outcome meeting the definition of a SAE (see [section 7.1.4, Serious Adverse Events](#)) must also be reported on the VSAE Report Form.

### **7.1.7 Safety Laboratory Measurements**

This study has no safety laboratory measurements.

### **7.2 Efficacy Assessment**

This study has no efficacy measurements.

### **7.3 Immunogenicity Assessment**

For the primary and secondary immunogenicity objectives, the GBS serotype-specific (Ia, Ib, III) IgG antibody responses in the serum will be determined by ELISA.

Original samples from subjects who participated in the V98\_06 study who are also participating in this V98\_06E1 study may be re-tested for the purposes of consistency in the ELISA assay being used to analyze the samples collected in this extension study.

The GBS serotype-specific IgG ELISAs in sera will be carried out by Clinical Laboratory Sciences, GlaxoSmithKline, Marburg, Germany.

The diphtheria-specific IgG antibody levels will be measured by ELISA. Testing will be conducted by a designated, qualified external laboratory.

Functional activities of anti-GBS antibodies will be measured by opsonophagocytic killing assay (OPK). Testing will be conducted by a designated qualified external laboratory.

Technical details (or instructions) for specimen collection, processing and shipment will be described in Clinical Specimen Lab Manual which will be made available to site

personnel after site initiation (e.g. refer to the Clinical Specimen Lab Manual in the investigator site file).

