### **8.1.2.3 Secondary Immunogenicity Endpoint(s)**

The secondary immunogenicity endpoints are:

The percentage of subjects reaching pre-defined sequential serotype-specific (Ia, Ib and III) serum antibody levels as measured by ELISA at other time points and in subgroups of subjects defined by their pre-vaccination serotype-specific GBS antibody LLQ status in the V98\_06 study (or the V98\_06E1 study for the naive group).

The serotype-specific (Ia, Ib, and III) geometric mean concentrations (GMCs) as measured by ELISA at days 31 and 61 post-vaccination in study V98\_06E1 and in the subgroups of subjects defined according to their pre-vaccination serotype-specific GBS antibody LLQ status in the V98\_06 study (or V98\_06E1 study for the naive group).

The within subject geometric mean ratio (GMR) of serotype-specific (Ia, Ib & III) serum antibody levels as measured by ELISA at day 31 and 61. The GMRs will be determined relative to pre-vaccination in V98\_06E1 and separately relative to pre-vaccination in V98\_06 for all groups except the naive group. The GMRs will also be determined for subgroups of subjects defined according to their pre-vaccination serotype-specific GBS antibody LLQ status in the V98\_06 study or V98\_06E1 study for the naive group.

Reverse cumulative distribution function (RCDF) curves of serotype-specific (Ia, Ib and III) serum antibody levels, as measured by ELISA, at pre-vaccination in V98\_06 study or V98\_06E1 study for the naive group, vaccination, day 31 and day 61 post-vaccination in all subjects and by pre-vaccination serotype-specific GBS antibody LLQ status in the V98\_06 study or V98\_06E1 study for the naive group.

The anti-diphtheria geometric mean antibody concentrations measured by ELISA for samples collected before the first vaccination with GBS Trivalent Vaccine in the V98\_06 study or V98\_06E1 study for the naive group and on day 61 post-vaccination in V98\_06E1.

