### **8.3.7 Subgroups**

Subgroups of subjects will be created based on the ELISA serotype-specific (Ia, Ib, III) antibody LLQ status prior to initial vaccination in study V98\_06 (or V98\_06E1 for the naive group).

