##### **8.4.3.3.3 Statistical Methods**

*GBS*

*Percentages at Day 31 and RCDFs*

The frequency and percentages of subjects with serotype-specific concentrations above a set of pre-defined sequential serotype-specific (Ia, Ib and III) serum antibody levels and associated two-sided 95% Clopper-Pearson CIs will be computed for each study group, for the MF59 study groups combined, for the unadjuvanted and Alum adjuvanted study groups combined, and the placebo and naive groups combined for concentrations at day 31 post-vaccination. Differences in percentages between study groups will be computed and two-sided 95% confidence intervals for the difference constructed using the method of Miettinen and Nurminen. Differences in percentages between study groups will be computed and two-sided 95% confidence intervals for the difference constructed using the method of Miettinen and Nurminen. The following treatment group comparisons will be examined: each 5µg group compared to the placebo group from study V98\_06 and separately to the naïve group; the combined MF59 groups compared to the combined

placebo and naïve groups; and, the combined unadjuvanted and Alum groups compared to the combined placebo and naïve groups.

Similar analyses will be performed for the subset of subjects defined by the pre vaccination serotype-specific GBS antibody LLQ status in the V98\_06 study or V98\_06E1 study for the naïve group.

The percentages of subjects with serotype-specific concentrations above a set of pre-defined sequential serotype-specific serum antibody levels will be graphically displayed as RCDFs.

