#### *Geometric Mean Concentrations*

Before any statistical analysis that assumes normally distributed observations, antibody concentrations will be  $\log_{10}$ -transformed. Individual concentrations below the limit of quantitation (LLQ) will be set to half that limit.

The logarithmically (base 10) transformed antibody concentrations will be modeled using an analysis of covariance (ANCOVA) model with a qualitative factor for vaccine group and  $\log$  (base 10) pre-vaccination concentration in study V98\_06, or V98\_06E1 for the naïve group, as a covariate. As this is a single-center study, site is not included as a covariate. Response in the V98\_06 study was different in those with a pre-vaccination concentration below the LLQ, so pre-vaccination concentration is included. The adjusted GMC and the two-sided, 95%, confidence intervals (CIs) of the GMC will be calculated based on this model. The ratio of GMCs and the corresponding two-sided, 95% CI will also be calculated based on this model. The adjusted GMC and two-sided 95% CIs will be constructed by exponentiation (base 10) of the least square means of the logarithmically transformed (base 10) antibody concentration. The model can be written as:

$$\log_{10}(y_{ik}) = \mu + \alpha_i + \beta x_{ik} + \varepsilon_{ik}$$

where  $\mu$  represents a common overall mean,  $\alpha_i$  represents the vaccine group  $i$  effect (where vaccine group is either the V98\_06 vaccine group, or naïve),  $\beta$  represents the common slope for the  $\log_{10}$  prevaccination concentration,  $x_{ik}$  for subject  $k$  in vaccine group  $i$ , and  $\varepsilon_{ik}$  represents random error for subject  $k$  in vaccine group  $i$ . A similar approach will be used in the subgroups based on pre-vaccination LLQ status.

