#### *Geometric Mean Ratios*

The logarithmically (base 10) transformed within subject ratio of antibody concentrations (post vaccination / baseline) will be modeled using an analysis of variance model with a qualitative factor for vaccine group (vaccine received in study V98\_06 or naïve). The

adjusted GMR and the two-sided, 95% CIs of the GMR will be calculated based on this model. The model can be written as:

$$\log_{10}(y_{ik}) = \mu + \alpha_i + \varepsilon_{ik}$$

where  $\mu$  represents a common overall mean,  $\alpha_i$  represents the vaccine group  $i$  effect and  $\varepsilon_{ik}$  represents random error for subject  $k$  in vaccine group  $i$ . The baseline value is either the pre-vaccination concentration in study V98\_06 or the pre-vaccination concentration in study V98\_06E1 as both are to be used in separate analyses. A similar approach will be used in the subgroups based on pre-vaccination LLQ status.

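### Does leaving the re-testing of V98_06 sera optional, with no named result or LLQ, undermine the secondary GBS ELISA analyses?

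*Combined protocol and SAP*

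**What the plan says.** Section 7.3 allows the V98_06 samples of subjects who join the extension to be re-tested: they "may be re-tested for the purposes of consistency in the ELISA assay being used to analyze the samples collected in this extension study". It adds no trigger, scope or order of precedence.

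V98_06 baseline results, or LLQ status, enter these analyses:

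- **GMC model (8.4.3.3.3).** The covariate is the log10 pre-vaccination concentration, from V98_06 for returning subjects and from V98_06E1 for naive subjects. The reason given is that response in V98_06 "was different in those with a pre-vaccination concentration below the LLQ, so pre-vaccination concentration is included". The substitution rule is "Individual concentrations below the limit of quantitation (LLQ) will be set to half that limit".
- **GMR (8.1.2.3 and 8.4.3.3.3).** The ratio is taken against each study's baseline, "as both are to be used in separate analyses". The V98_06 version is planned "for all groups except the naive group".
- **LLQ subgroups (8.3.7).** "Subgroups of subjects will be created based on the ELISA serotype-specific (Ia, Ib, III) antibody LLQ status prior to initial vaccination in study" V98_06, or in V98_06E1 for the naive group. Section 8.4.3.3.3 carries this into the percentages: "Similar analyses will be performed for the subset of subjects defined by the pre vaccination serotype-specific GBS antibody LLQ status".
- **RCDFs (8.1.2.3).** "Reverse cumulative distribution function (RCDF) curves of serotype-specific (Ia, Ib and III) serum antibody levels, as measured by ELISA, at pre-vaccination in" V98_06 and at the later time points.

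LLQ status also defines the exploratory OPK subgroups (8.1.3.3) and a baseline summary (8.4.1). No LLQ value is given. Sections 8.3.8 and 8.4.2.1.2 refer to a statistical analysis plan for exclusionary deviations and implausible measurements; no separate plan is among the documents.

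**The concern.** Once a serum is re-tested, the subject has two valid baseline results, and the protocol does not say expressly which one counts. Naive subjects can only have extension-era baselines. If the original V98_06 values were kept, one covariate and one LLQ definition would combine results from two testing periods.

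If the assay or its LLQ had changed in between, the V98_06-baseline GMR would mix assay change with immune response. Below LLQ would also mean one thing for returning subjects and another for naive subjects. The half-LLQ rule sharpens this: for subjects below LLQ at baseline and above it afterwards, the V98_06-baseline GMR is the post-vaccination GMC divided by LLQ/2, so it moves in direct proportion to the limit used. LLQ subgroups are part of a secondary objective (2.2), and an unwritten choice could in principle be made with results in view.

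**Working it through.** The plan gives no figure to reproduce on this point. The check sets out what is exposed, how 7.3 reads, and how large an effect could be under assumed inputs.

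**1. What is exposed.** The primary endpoint (8.1.1.3) uses day 61 extension samples only and is untouched. The all-subject GMR against the V98_06E1 baseline is also untouched. A uniform assay shift cancels, to a close approximation, in adjusted GMC contrasts among the five V98_06 groups. What remains is the V98_06-baseline GMR, the RCDF at V98_06 baseline, the LLQ subgroups and any adjusted contrast with the naive group.

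**2. How 7.3 reads.** Its only stated reason for re-testing is consistency with the assay used on the extension samples. Re-testing and then analysing the original value would not serve that purpose. The natural reading is that a re-test value replaces the original. The GMC text likewise speaks of one limit, not two.

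**3. Assumptions for size.** The documents give no assay CV, shift, LLQ, share below LLQ, SD or slope. Assumed: log10 baseline SD 0.6, residual SD 0.5, slope b = 0.5, 30% below LLQ, no true group difference.

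**4. Assay unchanged.** Two independent errors are added to the same true value, each with SD = sqrt(ln(1+CV²))/ln(10).

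| CV | below on original only | below on re-test only | total | of 200 returning subjects |
|---|---|---|---|---|
| 15% | 2.1% | 2.1% | 4.2% | about 8 |
| 25% | 3.45% | 3.45% | 6.9% | about 14 |
| 35% | 4.7% | 4.7% | 9.5% | about 19 |

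The movements cancel. The GMC of the below-LLQ subgroup, original classification against re-test, has ratio 1.000 at every CV. With 60% below LLQ, total disagreement is 4.7%, 7.7% and 10.5%, again balanced. The choice of set causes no bias, and naming a set would not reduce the noise.

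**5. Assay changed and original values kept.** Let the V98_06 assay read k times the extension assay.

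- Share classed below LLQ = Φ(z₀.₃₀ − log10(k)/0.6). For k = 1/2: Φ(−0.524 + 0.502) = 49%. For k = 2: Φ(−1.026) = 15%. Naive subjects stay at 30%.
- V98_06-baseline GMR, after half-LLQ substitution: ×1.74, 1.40, 1.17 for k = 1/2, 1/1.5, 1/1.2, and ×0.85, 0.69, 0.53 for k = 1.2, 1.5, 2.
- Below-LLQ GMC, returning/naive = 10^(b(E₁−E₀)) with E = −0.6·φ(z_P)/P: 1.27, 1.15, 1.07 and 0.93, 0.86, 0.77.
- LLQ alone halved or doubled, membership allowed to change: below-LLQ GMR ×1.53 or ×0.64.
- Adjusted GMC ratio to naive, by simulation with 40 per V98_06 group and 20 naive: 1.39 (k = 1/2) and 0.72 (k = 2). The 95% CI factor is 10^(1.96 × 0.5 × sqrt(1/40 + 1/20)), about 1.9, so the bias lies inside the interval. The interval misses the truth in 16% to 18% of runs at a twofold shift. With 40 or 15 per group, it misses in 6.5% to 8.3% at 1.5-fold and 5.1% to 6.6% at 1.2-fold, against 5% nominal. The GMC section names no comparator, so this contrast may not be reported at all.

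Step 5 needs two things together: a change that the documents do not show, and an analyst who keeps the old values despite the purpose written in 7.3.

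**The case for a change.** The best case for acting is that an exploratory label does not excuse an ambiguous quantity. From the protocol alone a reader cannot tell which baseline result or which LLQ lies behind a reported V98_06-baseline GMR or a below-LLQ subgroup. The sponsor itself raises assay consistency and then leaves its handling open. V98_06 response differed by LLQ status, so membership is not neutral, and a partial re-test could mix two sets of values. Wording costs little.

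That the text is incomplete stands: whether re-testing happens, and for whom, is not written. The rest is weaker. The open label in 3.3 concerns treatment, and every subject receives the same vaccine; it says nothing about who sees ELISA results or when re-testing is decided. With no hypotheses and no success criteria there is little to gain by choosing between results. Assay versions and limits are ordinary analysis-plan or laboratory content, and the missing plan may well hold them, although the protocol does not promise that.

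A fuller rule also has a price. A trigger based on an assay shift needs a numerical limit for which the documents offer no basis. A bridging check on sera above LLQ would not test classification at the LLQ. A strict ban on mixing values, combined with the complete-case analysis in 8.4.3.3.3, would drop returning subjects without usable stored serum from a sample that section 1.2 already expects to be limited.

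**Conclusion.** No change to the plan is needed. The rule is unwritten, not wrong. Section 7.3 gives the reason for re-testing, and that reason points to one sensible handling: where sera are re-tested, the re-test values and the limit of the current assay serve as baseline; otherwise the originals do.

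The gap reaches only secondary and exploratory estimates that are descriptive (8.4.3.3.1), in a study that section 1.2 calls exploratory and section 8.5 says is not powered. The primary day 61 percentages are unaffected. With an unchanged assay the effect is 4% to 9% of subjects changing LLQ class, evenly in both directions, with no shift in the subgroup mean. Factors up to 1.74 or down to 0.53 in the V98_06-baseline GMR arise only with an assumed twofold shift and original values retained. All sizes rest on the assumed CV, SD, slope and share below LLQ. The view would differ if the assay or LLQ were known to have changed and the original values were nonetheless analysed; nothing in the documents shows either.
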